10.7. Appendix 7: Daily Asthma Symptom Score

Each morning subjects will record in the eDiary an assessment of the severity of their asthma symptoms during the prior 24 hours using the following scale:

- 0 = No symptoms
- 1 = Symptoms for one short period
- 2 = Symptoms for two or more short periods
- 3 = Symptoms for most of the prior 24 hours which did not affect my ability to carry out my daily activities
- 4 = Symptoms for most of the prior 24 hours which did affect my ability to carry out my daily activities
- 5 = Symptoms so severe that I could not go to work/school or complete my normal daily activities

10.8. Appendix 8: Prohibited Medications and Treatments

Bronchial thermoplasty and radiotherapy are excluded in the 12 months prior to Screening visit and throughout the study. Continuous positive airway pressure, oxygen therapy, or allergen immunotherapy may not be initiated after the Screening visit.

The following medications must be washed out for the period noted in the table below and prohibited throughout the study as they may interfere with endpoint interpretation.

Medication	Washout time prior to Screening visit
mepolizumab, reslizumab, benralizumab, omalizumab, dupilumab	5 half-lives (~4 months)
Immunosuppressive medications such as those listed below (not all inclusive)	
regular use of oral corticosteroid	1 month
intramuscular long-acting depot if used to treat a condition other than asthma	3 months
methotrexate, azathioprine, imatinib, sulfasalazine, cyclosporine	1 month
chemotherapy used for conditions other than asthma	6 months

GB001 is metabolized at least in part by CYP3A4, hence the need to restrict the usage of known CYP3A4 inducers and inhibitors. Thus, the following is a non-exhaustive list of medications and drink/food which may inhibit or induce CYP3A4 activities that will be prohibited 14 days prior to randomization through the Safety Follow-up visit:

Prohibited Food/Drink (list is not all inclusive)	Washout time prior to Randomization
Grapefruit or grapefruit juice	14 days
Seville Oranges	
Marmalade	
Moderate or Strong Inhibitors of CYP3A4 (list is not all inclusive)	Washout time prior to Randomization
ciprofloxacin	14 days
erythromycin, clarithromycin, telithromycin	
fluconazole, itraconazole, ketoconazole, posaconazole, voriconazole, oral clotrimazole	
Diltiazem	
aprepitant	
verapamil	
nefazodone	
curcumin	
Moderate or Strong Inducers of CYP3A4 (list is not all inclusive)	Washout time prior to Randomization
carbamazepine	14 days
phenytoin	
rifampin	
modafinil	
St. John's wort	

A more comprehensive but still non-exhaustive list of prohibited medications and drinks/food to prevent potential metabolic drug-drug interactions will be provided in a manual to study sites.

10.9. Appendix 9: Restricted Medications and Treatments

Restricted medications are defined as medications which should be avoided, if possible; however, they are not prohibited during this study if stable for at least one month before screening. If such medications are required, consider switching to another medication in the class that is not restricted.

Medications known to be associated with drug-induced liver injury	
Allopurinol	Interferon beta
Amiodarone	Isoniazid
Amoxicillin-clavulanate	Methyldopa
Anabolic steroids	Minocycline
Atorvastatin	Nevirapine
Carbamazepine	Nimesulide
Chlorpromazine	Nitrofurantoin
Oral contraceptives	Propylthiouracil
Dantrolene	Quinidine
Diclofenac	Pyrazinamide
Didanosine	Simvastatin
Disulfiram	Sulfamethoxazole/Trimethoprim
Flucloxacillin	Sulfonamides
Halothane	Sulindac
Hydralazine	Telithromycin
Ibuprofen	Ticlopidine
Interferon alpha/Peginterferon	Valproate

Source: [Björnsson, 2016](#).

10.10. Appendix 10: Estimated Clinical Comparability of Medium and High Doses of Inhaled Corticosteroids

Medication	Medium Dose mcg/day	High Dose mcg/day
Beclomethasone dipropionate CFC	>500-1000	>1000
Beclomethasone dipropionate HFA	≥200-399	≥400 ^a /320 ^b
Beclomethasone extra-fine/LABA combination	≥200-399	≥ 400
Budesonide DPI	>400-800 ^a / ^{>} 320--400 ^b	>800 ^a /640 ^b
Budesonide/LABA combination	Ex-United States: ≥400-800 ^a / [≥] 320-640 ^b	Ex-United States: >800 ^a /640 ^b
	United States: 320 -639 ^b	United States: ≥ 640 ^b
Ciclesonide	>160-320	>320
Fluticasone furoate/LABA DPI	92 ^c /100	184 ^c /200
Fluticasone propionate/formoterol MDI	>230-460 ^b /250-500 ^a	>460 ^b /500 ^a
Fluticasone propionate DPI	>250-500	>500
Fluticasone propionate/LABA HFA	>230-460 ^b /250-500 ^a	>460 ^b /500 ^a
Fluticasone propionate/LABA DPI	>250-500 /233-465 ^c	> 500 /465 ^c
Mometasone furoate	>220-440 />200-400 ^c	>440 /400 ^c
Mometasone furoate/LABA	200-400 ^c	>400 ^c
Triamcinolone acetonide	>1000-2000	>2000

Abbreviations: CFC, chlorofluorocarbon propellant; DPI, dry powder inhaler; HFA, hydrofluoroalkane propellant; ICS, inhaled corticosteroid; NA, not applicable

^a ex-valve

^b ex-actuator

^c dose delivered

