2.3. Benefit/Risk Assessment

2.3.1. GB001 Risk/Benefit Assessment

GB001, an oral DP₂ antagonist, is being developed as a maintenance therapy in asthma. Despite the recent availability of injectable biologics to manage asthma patients with poor control and exacerbations, there continues to be a paucity of oral agents to help manage and control asthma. The mechanism of GB001 is to antagonize the DP₂ receptor and thereby reduce the T helper cell type 2 (Th₂) response while affecting other cells relevant in the inflammatory and allergic cascade with corresponding improvements in asthma control, lung function and exacerbations (Hall, 2015; Gonem, 2016; Bateman, 2017). Ultimately these physiologic effects could result in an improvement in the overall quality of life of patients with moderate to severe asthma.

As of 29 August 2019, a total of 459 subjects have received at least 1 dose of GB001 at any dose level. Drug induced liver injury is considered a potential risk of GB001 due to the occurrence of two Hy's Law cases, one was a liver disorder (preferred term) in a healthy subject at 160 mg in Study PTR-36-101 and one was hepatic enzyme increased (preferred term) in the current study which remains blinded. Details are provided in the IB. Liver monitoring is critical for the safe management of subjects. Investigators should have a low threshold for discontinuing study drug with any suspicion of drug-induced liver injury. Safety will be closely monitored by the Sponsor and the Independent Data Monitoring Committee (IDMC).

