5. STUDY POPULATION

Prospective approval of protocol deviations to recruitment and enrollment criteria, also known as a protocol waiver or exemption, is not permitted.

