9. **Immunodeficiency:** A known immunodeficiency, including that due to human immunodeficiency virus (HIV), other than that explained by systemic corticosteroid use.
10. **Investigational medications:** Subjects who have received treatment with an investigational medication within the past 30 days or within 5 half-lives of the medication, whichever is longer, prior to Screening visit. (This also includes investigational formulations of marketed products.)
11. **DP₂ (CRTh2) antagonist studies:** Participated in another DP₂ (CRTh2) antagonist study in the 12 months prior to Screening visit or known prior intolerance or inadequate response in a prior DP₂ antagonist study.
12. **Receiving prohibited medications or treatments:** (refer to Appendix 8, [Section 10.8](#), for more details)
 - a. Regular use of systemic corticosteroids or immunosuppressive therapies including methotrexate or azathioprine
 - b. Monoclonal antibodies used in the treatment of asthma such as reslizumab, mepolizumab, omalizumab or benralizumab
 - c. Medications, food or drink that are moderate or strong CYP3A4 inhibitors or inducers
 - d. Medications that have the potential for interaction with GB001
 - e. Bronchial thermoplasty and radiotherapy are excluded in the 12 months prior to Screening
13. **Prior participation in a study with GB001:** Subjects who previously participated in a study with GB001 (also named PTR-36 or ADC3680) are not eligible for this study.
14. **Hypersensitivity:** A known sensitivity to GB001 or any of its excipients. Patients with rare hereditary problems of galactose intolerance, the Lapp lactase deficiency, or glucose-galactose malabsorption are not eligible for this study. Subjects with mild-moderate lactose intolerance are not excluded.
15. **Pregnancy:** Subjects who are pregnant or breastfeeding. Subjects should not be enrolled if they are planning to become pregnant during the time of study participation. A serum pregnancy test is required of all females of child-bearing potential at Screening.
16. **Adherence:** Subjects who have a known lack of adherence to controller medications.
17. **Body Mass Index (BMI):** BMI is ≥ 40 kg/m².
18. Have any other condition or reason that, in the opinion of the Investigator, would prohibit the subject from participating in the study, including participation in another clinical trial while participating in this study.

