6.4. Concomitant Therapy

Subjects should remain on their current SOC therapy (ie, medium or high dose ICS plus additional controller therapy) through the duration of their time on study. If a subject experiences asthma worsening as defined in [Section 4.1.1](#) or if a subject discontinues IP or withdraws from the study due to lack of efficacy, SOC therapy may be adjusted, as needed, at the discretion of the Investigator.

Any medication or vaccine (including over-the-counter or prescription medicines, vitamins, and/or herbal supplements) that the subject is receiving at the time of enrollment or receives during the study must be recorded along with:

- Reason for use
- Dates of administration including start and end dates
- Dosage information including dose and frequency

The Medical Monitor should be contacted if there are any questions regarding concomitant or prior therapy.

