6.4.2. Restricted Medications

Restricted medications are defined as medications which should be avoided, if possible; however, they are not prohibited during this study if stable for at least one month before screening. If such medications are required, consider switching to another medication in the class that is not restricted. Please refer to Appendix 9 ([Section 10.9](#)) for restricted medications.

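### Section 6.4.2 and Appendix 9 permit stable use of carbamazepine and telithromycin, which Exclusion 12c and Appendix 8 prohibit

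*Protocol*

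**What the plan says.** The protocol sorts problem medications into two classes.

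**Restricted.** Section 6.4.2 sets the rule: "Restricted medications are defined as medications which should be avoided, if possible; however, they are not prohibited during this study", on condition that use was stable for at least a month before screening. Appendix 9 repeats it ("they are not prohibited during this study if stable for at least one month before screening") above a table of drugs linked to liver injury. The entries include "Carbamazepine" and telithromycin. The table has no footnote, no drug-level exception and no pointer to Appendix 8.

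**Prohibited.** Exclusion 12c bars subjects receiving "Medications, food or drink that are moderate or strong CYP3A4 inhibitors or inducers" and refers to Appendix 8 for details. Appendix 8, which does not claim to be complete, covers "medications and drink/food which may inhibit or induce CYP3A4 activities that will be prohibited 14 days prior to randomization through the Safety Follow-up visit". Telithromycin appears there among the inhibitors and carbamazepine among the inducers, each with a 14-day washout before randomization. Stable use is not an exception.

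Section 5 says that advance approval of a deviation from the enrolment criteria, "also known as a protocol waiver or exemption, is not permitted". Section 6.4.1 sends the reader to Appendix 8 for prohibited drugs but does not say which appendix prevails when a drug is on both lists. No other section says so either.

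**The concern.** The protocol gives opposite answers for the same two drugs. A coordinator with a candidate on long-term carbamazepine who opens Section 6.4.2 or Appendix 9 reads that the drug may continue. One who opens Exclusion 12c or Appendix 8 reads that the subject is ineligible.

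The reason for the ban is pharmacokinetic: Appendix 8 says GB001 is partly metabolized by CYP3A4. A month of stable use does not remove that reason; it means the interaction is present throughout treatment. In a dose-ranging trial that measures plasma concentrations, an affected subject may not have the exposure that the assigned dose is meant to give.

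There is also a safety setting to consider. Section 2.3.1 states that "Drug induced liver injury is considered a potential risk of GB001", and both drugs are on the protocol's own list of agents linked to liver injury.

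**Working it through.** No sample size, power or error-rate figure is involved, so there is no figure in the plan to reproduce. The check compares the two lists and then the two time windows.

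**Step 1: count the lists.**
- Appendix 9: 17 rows of 2 entries, 17 × 2 = 34.
- Appendix 8, CYP3A4 inhibitors: ciprofloxacin (1); three macrolide or ketolide antibiotics (3); six azole antifungals (6); diltiazem, aprepitant, verapamil, nefazodone and curcumin (5). Total 1 + 3 + 6 + 5 = 15.
- Appendix 8, CYP3A4 inducers: carbamazepine, phenytoin, rifampin, modafinil, St. John's wort. Total 5.
- CYP3A4 agents named, leaving aside food and drink: 15 + 5 = 20.

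**Step 2: match the names.** Exactly two names are on both lists: carbamazepine and telithromycin. Adding the ten other drugs named in Appendix 8 (five biologics and five immunosuppressive agents) makes 30 names and produces no further match.

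**Step 3: compare the rules for those two drugs.**

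| | Section 6.4.2 and Appendix 9 | Exclusion 12c and Appendix 8 |
|---|---|---|
| Carbamazepine | Allowed on study if stable for a month before screening | Prohibited (inducer) |
| Telithromycin | Allowed on study if stable for a month before screening | Prohibited (inhibitor) |
| Exception | None stated | None for stable use |
| Status | Concomitant-medication rule | Eligibility criterion, no waiver |

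**Step 4: see whether timing could reconcile them.** The Run-in lasts 2 to 6 weeks, so the 14-day point before randomization falls at or after Screening. A subject who was stable before Screening and carries on, as Appendix 9 allows, is taking the drug throughout the banned window. That window is 2 weeks before randomization + 24 weeks of treatment + 4 weeks of follow-up = 30 weeks. The two rules cannot both be followed for a subject who continues the drug.

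**Step 5: decide which rule is right.** Exclusion 12c is an eligibility criterion, it cites Appendix 8, waivers are ruled out, and the stated reason for the ban applies equally to stable users. Prohibition is the correct answer, so the permission is the text in error.

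**The case against.** The strongest reply is that the operative rule is already clear. A site cannot randomize properly without checking Exclusion 12, Section 6.4.1 stands immediately before 6.4.2, and the two lists serve different purposes. Appendix 9 flags liver risk and Appendix 8 flags an interaction, so a drug can carry both flags, with the stricter rule applying. Appendix 8 also promises sites a fuller list in a manual, and Section 6.4 offers a further route: "The Medical Monitor should be contacted if there are any questions regarding concomitant or prior therapy".

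Part of this stands. A careful site would reach the right answer, and the manual, which is not available here, may help. But the permission is worded for the whole study, not just for Appendix 9, and in that form it is untrue for these two drugs. Nothing in the protocol states that the stricter list prevails. The Medical Monitor route depends on the site having a question, and an express permission gives it little reason to ask.

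Three limits should be accepted:
- **Scope.** The permission covers only drugs stable for a month before screening. Telithromycin is unlikely to be used that way, so long-term carbamazepine is the realistic case. This is a judgement, not a figure from the documents.
- **Liver risk.** Being on the liver list is not why these two are banned, since the other 32 entries are allowed if stable. As an inducer, carbamazepine would be expected to lower GB001 exposure. Liver chemistry is also checked at Weeks 1, 2, 3 and 4 and at each later visit. The liver point is context; the interaction carries the argument.
- **Analysis.** SAP Section 4.4 already lists Exclusion 12 among the reasons for leaving the per-protocol population.

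**Conclusion.** The concern holds. The statement that stable restricted drugs may continue is wrong for carbamazepine and telithromycin, and it sits in a rule that sites act on. It could lead a site to enrol or keep a subject whom Exclusion 12c bars.

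The extent is 2 of 34 entries. How many subjects are affected, and how far their GB001 exposure would change, cannot be taken from the documents; the number is probably very small. No effect is claimed on the primary ITT analysis, the power, the sample size or the per-protocol definition. The conclusion rests only on the current text of both appendices, Section 6.4.2 and Exclusion 12c, and on the absence of any precedence statement. It should be corrected because the written permission contradicts an eligibility criterion and the correction costs almost nothing.

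**What to change.** Preferred: add one clause to Section 6.4.2 and to the opening paragraph of Appendix 9, saying that the permission does not apply to any drug prohibited under Appendix 8 or Exclusion 12, which govern. Because the CYP3A4 lists in Appendix 8 are expressly incomplete, the clause also covers overlaps that are not visible from the names printed there.

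Alternative: delete carbamazepine and telithromycin from Appendix 9. This removes the two known conflicts but does not guard against others.

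Either way, send sites a short notice. Exclusion 12, Appendix 8 and the per-protocol criteria stay as they are. The cost is one clause in two places, or two deleted names, plus the notice, with no change to design, sample size or analysis.

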10.11. Appendix 11: Assessment of Hair Loss

Questionnaire to Assess Patient Perceptions of Hair Growth

1. Do you lose hair to the point that this is concerning? Yes No
2. Do you have any bald spots? Yes No

Note: If the subject answered "Yes" to any of the questions above, the site will complete the graphical visual assessment for male and female subjects (Norwood and Savin Scales), respectively.

In those subjects who completed the above information, **at the end of the study** (Last IP Visit) the following questions should be completed, please check only one box:

- a. Since initiation of the study, I noticed my bald spot is getting smaller:

Strongly agree	
Agree	
A little better	
The same	
A little worse	
Somewhat worse	
A lot worse	

- b. Overall, since initiation of the study, I noticed that the growth of my hair is:

Greatly increased	
Moderately increased	
Slightly increased	
The same	
Slightly decreased	
Moderately decreased	
Greatly decreased	

10.12. Appendix 12: Guidance to Address a Pandemic or Other Global Health Emergencies and Potential Impact on the Clinical Study

In the occurrence of a global health pandemic affecting the conduct of the ongoing study, such as the COVID-19 pandemic, study conduct may be adjusted due to subjects being in self-isolation/quarantine, limited access to public places (including hospitals) due to the risk of spreading infections, and health care professionals being committed to critical tasks (FDA, 2020; EMA, 2020; Health Canada, 2020; MHRA, 2020).

Adjustments to the GB001-2001 protocol may be made as described below, in line with global regulatory authorities guidance in order to ensure the safety of study participants, maintain compliance with GCP, and minimize the risks to trial integrity during the COVID-19 pandemic (FDA, 2020; EMA, 2020; Health Canada, 2020; MHRA, 2020). Member states within the National Competent Authorities may issue their own guidance requiring country specific recommendations to be followed.

- In the case of missed visits due to COVID-19 (or other health pandemic) related reasons:
 - The site should make every effort to contact the subject to confirm and document the reason for the missed visit, and at minimum evaluate AEs/SAEs, concomitant medications, and asthma exacerbations in order to assess subject status.
 - The subject should continue to collect the daily AM PEF and eDiary responses on the eDiary. The eDiary will provide an alert to potential asthma worsening, as described in [Section 4.1.1](#). In the event of an alert, the subject should contact the site staff as soon as practical to assess the subject's asthma status.
- Alternative methods of collecting study assessments may be considered where possible:
 - Questionnaires, including ACQ-5, AQLQ, and SNOT-22, may be self-administered by the subject at home.
 - In certain situations, with Sponsor approval, a local laboratory may be used.
- Alternative methods of supplying IP to study subjects (eg, direct-to-patient shipment from site) may be considered where possible.
 - With prior sponsor approval, IP may be supplied via alternative methods provided that laboratory assessments are able to be performed prior to the delivery of IP. In all cases, study subjects must provide consent for alternative delivery methods. Documentation of consent will be captured in the subject's study records.

10.13. Appendix 13: Abbreviations

Abbreviation Term	Description
ACQ	Asthma Control Questionnaire
AE	adverse event
ALT	alanine aminotransferase
AM	morning
ANCOVA	analysis of covariance
AQLQ-S	Asthma Quality of Life Control Questionnaire (standardized)
AST	aspartate aminotransferase
BMI	body mass index
BUN	blood urea nitrogen
CI	confidence interval
CIOMS	Council for International Organizations of Medical Sciences
CONSORT	Consolidated Standards of Reporting Trials
CPK	serum creatine phosphokinase
CRTh2	chemoattractant receptor-homologous molecule expressed on Th2
CSR	clinical study report
CTFG	Clinical Trial Facilitation Group
DILI	drug induced liver injury
DP ₂	prostaglandin D ₂ receptor
DPI	dry powder inhaler
EBC	exhaled breath condensate
EC	Ethics Committee
ECG	electrocardiogram
eCRF	electronic case report form
EDC	electronic data capture
eDiary	electronic diary
ES	extension study
EW	early withdrawal
FEF ₂₅₋₇₅	forced expiratory flow at 25% to 75%
FeNO	fractional exhaled nitric oxide
FEV ₁	forced expiratory volume in 1 second
FSH	follicle-stimulating hormone

Abbreviation Term	Description
FVC	forced vital capacity
GCP	Good Clinical Practice
GGT	gamma-glutamyl transferase
GINA	Global Initiative for Asthma
HAC	Hepatology Assessment Committee
HBcAb	Hepatitis B core antibody
HBsAg	Hepatitis B surface antigen
hCG	human chorionic gonadotropin
HIV	human immunodeficiency virus
HIPAA	Health Insurance Portability and Accountability Act
HPLC	high performance liquid chromatography
HRT	hormonal replacement therapy
IB	Investigator's brochure
ICF	Informed Consent Form
ICH	International Council for Harmonisation
ICS	inhaled corticosteroid
IDMC	Independent Data Monitoring Committee
IEC	Independent Ethics Committee
IgG	immunoglobulin G
IgM	immunoglobulin M
INR	international normalized ratio
IP	investigational product
IRB	Institutional Review Board
IRT	Interactive Response Technology
ITT	intent-to-treat
IUD	intrauterine device
IUS	hormone-releasing system
LABA	long-acting beta agonist
LAM	lactational amenorrhoea method
LAMA	long-acting muscarinic antagonist
LDH	lactate dehydrogenase
LTRA	leukotriene receptor antagonist

Abbreviation Term	Description
MCID	minimal clinically important difference
MDI	metered dose inhaler
OR	odds ratio
PD	pharmacodynamic
PEF	peak expiratory flow
PGD ₂	prostaglandin D ₂
PK	pharmacokinetic
PP	Per-protocol
PRO	patient reported outcomes
QTcF	Fridericia's correction formula for QT interval (interval between Q wave and T wave)
RBC	red blood cell
RNA	ribonucleic acid
SABA	short-acting beta-agonist
SAE	serious adverse event
SAP	Statistical Analysis Plan
SNOT-22	Sino-Nasal Outcome Test
SNP	single nucleotide polymorphism
SoA	schedule of activities
SOC	standard of care
SUSAR	suspected unexpected serious adverse reaction
TEAE	treatment-emergent adverse event
Th2	T Helper cell type 2
ULN	upper limit of normal
VOC	volatile organic compounds
WBC	white blood cell
WOCBP	women of childbearing potential

